7. STUDY-WIDE NUMBER OF SUBJECTS*

NA

8. STUDY-WIDE RECRUITMENT METHODS*

NA

9. STUDY TIMELINES*

Patient Subject Participant Involvement Timeline:

- ***Enrollment & Intake Visit: (Day 0)***
 - Informed consent
 - Non-biometric data – Contact information; Intake data points
 - Five-question Problem Areas in Diabetes (PAID-5) scale as well as the 17-question Diabetes Distress Scale (DDS) and supplemental questions will be administered
 - Device training (if randomized to CGM)

- Care coordination to DCOE (all patients)
- ***Outpatient Blood Sugar Monitoring (for intervention group only) (day 0-14)***
 - Continuous Glucose Monitoring – Sensor worn 24 hours a day for up to 14 days.
Data can be uploaded
- ***Follow Up: (~Day 14-21 post ED visit)***
 - Study team will meet patient at follow-up appointment
 - Biometric data – Downloaded
 - Non-biometric data – Five-question Problem Areas in Diabetes (PAID) scale as well as the 17-question Diabetes Distress Scale (DDS) and supplemental survey questions will be administered
 - Compensation (\$10)
- ***6 Months Follow up (no active patient involvement)***
 - Follow-up data points abstracted from electronic health record (EHR)

Provider Subject Participant Involvement Timeline:

- ***Follow Up: (~Day 14-21 post ED visit of patient subjects)***
 - Study team send survey questions to provider subjects immediately after they have a clinic encounter with a patient subject
 - This will be the only time point of participation for provider subjects

Study Timeline: We anticipate that recruitment will be complete by September 30, 2022. Primary data analysis will be complete by the end of March 2023.

10. STUDY ENDPOINTS*

Our primary outcome The primary outcomes will be the rate of attendance at the follow-up visit and be the change in diabetes-related quality of life as measured by the PAID-5 scale and the DDS.

Secondary outcomes will include A1c levels, recurrent ED or EMS utilization, hospitalizations, and major cardiovascular events. We will also query DCOE providers regarding their satisfaction with the program, including a question about whether the CGM data are helpful for each patient.

Expectation: Our hypothesis is that CGM use after ED discharge will reduce the clinic no-show rate and decrease diabetes-related distress compared to the group with care coordination only.

There are no primary or secondary safety measures being recorded for the purposes of this study.

Safety measures will include number of device questions/concerns expressed by subjects during enrollment through their two-week follow up appointment, reported blood sugar events,

(high/low values), and return visits to clinic/ED/hospitalizations within the 2 week window of enrollment.

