4. OBJECTIVES*

Our goal is to help people with diabetes who are treated and then discharged from the emergency department (ED) achieve better health outcomes. Specifically, we are interested in determining whether or not continuous glucose monitoring after ED discharge is useful.

People living with diabetes, particularly those from disadvantaged socioeconomic backgrounds, frequently seek medical care through the emergency department (ED), but coordinated longitudinal follow up is often lacking. Almost 1 in 10 ED visits are related to diabetes (1), and rates of diabetes-related ED utilization are negatively correlated with household income (2, 3). Being evaluated in the ED can be a powerful motivator for patients, but this window of opportunity can be missed if patient activation is low or if access to ongoing medical care is limited. Interventions designed to improve continuity between the ED and diabetes specialty care have shown promise in terms of reducing hospitalizations and medical expenditures (4), but even at institutions with these programs in place, recurrent diabetes-related ED visits continue to be a problem (5). Overall, diabetes care for people in the ED remains fragmented and poorly studied.

As we attempt to help people seeking care for diabetes in the ED, we plan to study the potential role of continuous glucose monitoring (CGM) in this novel context. In the outpatient setting, CGM has been shown to cause clinically significant reductions in hemoglobin A1c as well as hyper- and hypoglycemia (6-8). It can also improve a patient's self-management skills and understanding of how food and activity affect blood sugar (9). CGM use, however, has never been studied as a tool to help people being discharged from the ED. It will be valuable to assess its usefulness in this setting, as patients are at high risk of recurrent hyper- or hypoglycemia during this transitional window (10, 11) and may be more engaged than at other times.

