11. PROCEDURES INVOLVED*

Enrollment & Intake Visit of patient subjects:

- **Recruitment:** See Section 24. Research personnel will confirm subjects' pregnancy status by subject self report.
 - **Documents:**
 - **HIPAA Waiver**
 - **Info Sheet**
 - **Screening Log**
 - **Declined/Ineligible Log**
- **Consent:** See Sections 30 & 31
 - **Documents:**
 - **Consent**
 - **HIPAA Authorization**
- **Randomization:** Using the Redcap randomization module, patients will be randomized to the care coordination-only or care coordination plus CGM group
- **Master Code Contact Information:** Study Staff will obtain at least two ways (primary phone number and mailing address) to contact participants to schedule follow-up visits, completing a follow-up phone call if necessary, and to ensure the CGM equipment is returned.
 - **Documents:**
 - **Contact Info**
 - **Master Code**
- **Intake:** Study Staff will query EMRs to obtain the data points listed in the document below. Data collected will be verified with participants.
 - **Documents:**
 - **Intake Data- RA Facing**
 - **Intake Data- Patient Facing**
- **Device Training for intervention arm (CGM Arm only):** Half of the participants identified and enrolled as described above will be randomized to receive an unblinded CGM. We plan to use the 14-day Libre 2 CGM from Abbott. This device is a small disk (1.38 inches in diameter and 0.2 inches thick), and it weighs 0.18 ounces. After it is placed, a small (less than 0.4mm thick) sensor probe (not sharp) remains in the skin and can transmit continuous glucose data to a reader. The device can be submerged in water, and if it falls off, there will not be any significant bleeding. Study Staff will demonstrate the features and use of the CGM and sensor application (how the device should be worn, when it should be removed, the procedure to query the device for blood sugar readings using either a reader or smart phone application). After participants demonstrate an understanding of the use of the GCM, Study Staff will place the device on one of the participant's upper arms (patient choice) and monitoring will begin immediately after a

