- **Diabetes Center of Excellence Care Coordination:** Study Staff will follow up with ED provider to ensure that patients' have clinically indicated referral to diabetes center of excellence

→ **Appointment scheduling:** RA will make an appointment for the patient before ED discharge, if possible. If this is not possible, RA will contact the patient after discharge to arrange a follow-up appointment.

Outpatient Blood Sugar Monitoring: The CGM will be worn on the participants' upper arm continuously for 14 days (or until it falls off or the patient decides to remove it)

[figure not shown]
Visit #1 (~Day 14-21 Post-Discharge of patient subjects)

- **Documents:**
 - **Visit Data (RA facing)**
 - **Problem Areas in Diabetes (PAID-5) scale/Diabetes Distress Scale and supplemental questions**
 - **Fact sheet for provider subjects**
 - **Provider satisfaction survey**
- **CGM Data:** Biosensor data will be downloaded and reviewed
- **Material Collection:** Study Staff will collect CGM readers
- **Compensation:** Participants will be offered \$10 worth of gift cards to a retail store for completing visit #1.
- **Provider Survey:** immediately following an encounter with a patient subject, the provider taking care of each patient will be contacted by the study team as potential provider subjects. Potential provider subjects subsequently will be sent an email solicitation to participate in a Redcap survey. A fact sheet will be provided with that email. The survey will consist of 4 questions pertaining to their satisfaction with patient subject care coordination and/or their CGM utilization. Providers may be sent multiple surveys if they see multiple subjects who are enrolled in the study. This is the only involvement of the provider subjects.
- **No Shows:** *RAs will reach out to subjects who miss their follow-up appointment to (1) help them reschedule and (2) ask that they fill out the post-intervention questionnaire via an online link (or mailed paper copy or via phone, if desired)*

Follow up Data Collection (~6 months Post-Discharge)

- **Documents:**
 - **6 month follow up datasheet**
- **Data Collection:** The study team will query the EHR to collect follow up data points about enrolled subjects

Figure 1: Procedural Flow Sheet

t

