Sample Size: The primary outcomes are the clinic attendance rate and the change in diabetes-related distress, as measured by the Diabetes Distress Scale (DDS) and PAID-5 scale between the ED visit and the follow-up appointment date (19). Secondary outcomes include repeat ED/EMS utilization over 6 months, repeat hospitalizations, major cardiovascular events, and changes in hemoglobin A1c. For clinic attendance, we will aim to achieve attendance at 80% of the scheduled clinic visits. For a one-sided test at alpha=0.025 of a single proportion against a standard proportion (0.80), we will have 80% power to detect a difference of 0.13 (0.80 – 0.67) with a sample size of 83 subjects in the CGM group. Adjusted for 20% dropout, we will need approximately 100 subjects/group. For the DDS outcome, we will compare the change from baseline to the end of follow-up in the DDS between the two groups. Although we will fit the trajectory of the DDS change in each group using all DDS measures in a mixed effects model with repeated measures (MMRM), for simplicity in sample size estimation, we will calculate the sample size for an unadjusted comparison of the change between the two treatment groups. Based on a study of 267 subjects with diabetes (19), the standard deviation of the DDS was 1.0 across the three sites in that study. The DDS is a questionnaire of 17 questions, each scored on a Likert scale of 1 (not a serious problem) to 6 (serious problem), with the overall score calculated as the mean score across the 17 items. Thus, the range of the overall score is 1.0 – 6.0. With 100 subjects in each group, we can detect a difference of about 0.40 in the DDS change between the two groups. The literature on the DDS does not identify a clinically meaningful difference although Fisher, Polonsky, Hessler, Mullan (2012) suggest a difference of 0.5 as meaningful (20). Thus, our sample size will achieve power of greater than 80% to detect that difference.

Analysis Strategy: As indicated in the Sample Size section above, for the clinic attendance rate, we will conduct the initial unadjusted analyses using an exact test of the frequencies under the presumed population proportion (0.80) and the observed proportion. Adjusted analyses will be conducted using a logistic regression model for the proportion of clinic visits attended as the outcome in the intervention group with predictors including age, gender, time since diagnosis of diabetes, and other factors of interest.

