For the outcome of change in DDS, we will conduct the initial unadjusted analysis as described above in the Sample Size section. For adjusted analyses, we will include each DDS score in the longitudinal MMRM, so that we can model the trajectory of change as well as the individual changes over the period of follow-up. The time metric in this model will be the time (months) since study enrollment with predictors including age, gender, time since diagnosis of diabetes and other factors of interest. We will also investigate subgroups of interest using a Forest plot approach. We will plot the means and confidence intervals for the outcome for the two groups using Forest plots to display the total groups and subgroups of interest. We will also generate

longitudinal plots of A1c over time with the means and appropriate exact 95% confidence intervals at each time point. In addition, with the DDS trajectories available, we are able to use machine-learning approaches, such as growth mixture models, to identify clusters of patients with similar trajectories but who are not members of previously defined subgroups. Finally, we will conduct sensitivity analyses to determine if missingness of DDS scores are missing at random or missing not at random. For these analyses, we will use several methods, including the jump-to-reference imputation and the pattern mixture model approaches, to determine if the results using the sensitivity analyses are consistent with the MMRM results, indicating that the missingness is missing at random.

For the secondary outcomes, the change in HbgA1c will be modeled as for the DDS above. The other secondary outcomes can be modeled as binary outcomes and will be modeled as longitudinal logistic models.

Data Management Plan:

All study data will be recorded on a REDCap database established on a secure encrypted server on AWS. All access to the database will be through permissions established by the IT REDCap administrator. Investigators will have to log into the REDCap database to enter or view data. The REDCap database will be developed and implemented by the data management staff of the UMMS Quantitative Methods Core (QMC) with the direction of [name], QMC Director. Logic data checks will be built into the data entry process to help clean the data at entry. Quality control edits will be run to identify inconsistencies and questionable values in the data. The audit trail will be activated for the duration of the study.

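### The 6-month ED/EMS and hospitalisation models name no baseline covariate; prespecifying pre-index utilisation, readable from the EHR, is a cheap improvement of modest and uncertain size

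*Combined protocol and SAP*

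**What the plan says.** Section 10 (Study Endpoints) lists the outcomes: "Secondary outcomes will include A1c levels, recurrent ED or EMS utilization, hospitalizations, and major cardiovascular events". Section 13, Sample Size, sets the 6-month window for ED/EMS use: "Secondary outcomes include repeat ED/EMS utilization over 6 months, repeat hospitalizations, major cardiovascular events, and changes in hemoglobin A1c".

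The analysis of everything on that list except HbA1c is one sentence in Section 13, Analysis Strategy: "The other secondary outcomes can be modeled as binary outcomes and will be modeled as longitudinal logistic models". No covariate appears in it.

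Covariates are named elsewhere in the same section. The DDS model has "predictors including age, gender, time since diagnosis of diabetes and other factors of interest", the attendance model has a near-identical list, and HbA1c is to follow the DDS model. Neither list is said to apply to the utilisation outcomes.

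On data sources, Section 11 (Intake) states "Study Staff will query EMRs to obtain the data points listed in the document below", and for the 6-month follow-up "The study team will query the EHR to collect follow up data points about enrolled subjects". The intake item list is a separate form that is not reproduced in the text.

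**The concern.** Avoiding repeat ED visits is one of the programme's stated aims (Section 5). Section 4 acknowledges that even at institutions with ED-to-clinic programmes "recurrent diabetes-related ED visits continue to be a problem". If some patients use the ED habitually, past use should help predict use over the next 6 months. Section 11 describes REDCap randomisation and mentions no stratification, so with 100 patients per arm the number of frequent users in each arm is left to chance.

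A prognostic count taken before randomisation could absorb part of that chance variation with no patient contact. At stake are some power for the utilisation comparisons and protection against choosing covariates after the data are seen.

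**Working it through.** **1. The plan's own figures.** The documents give no event rate, power or sample size for the utilisation outcomes. The two sizing figures they do give reproduce:
- Attendance: n = [1.960·√(0.80·0.20) + 0.842·√(0.67·0.33)]² / 0.13² = 82.35, rounded up to the stated 83.
- DDS: (1.960 + 0.842)·1.0·√(2/100) = 0.396, the stated difference of about 0.40.

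Neither bears on the utilisation models. Every rate below is an assumption except the 100 per arm (Section 25).

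**2. A yes/no prior-use covariate.** Let a fraction π of patients have prior use, with event risks q1 (prior use) and q0 (none) and overall control risk p. Then R² = π(1−π)(q1−q0)² / [p(1−p)]. The standard error (SE) of the risk difference is multiplied by √(1−R²).

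Example: p = 0.30, π = 0.5, odds ratio (OR) for prior use 3, so q0 = 0.189 and q1 = 0.411. R² = 0.25·0.222²/0.21 = 0.059. The SE multiplier is √0.941 = 0.970, equivalent to 200/0.941 ≈ 213 patients instead of 200.

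Over p = 0.15 to 0.40 and π = 0.3 to 0.5:

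| Prior-use OR | R² | Fall in SE of risk difference |
|---|---|---|
| 1.5 | about 0.01 or less | 0.5% or less |
| 2 | 0.015–0.028 | 0.7–1.4% |
| 3 | 0.034–0.069 | 1.7–3.5% |
| 5 | 0.064–0.138 | 3.3–7.2% |

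In 6,000 simulated trials per setting (control risk 30%, 40% with prior use, conditional treatment OR 0.45), logistic power moved as follows:

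| Prior-use OR | Unadjusted | Adjusted |
|---|---|---|
| 1 | 64.6% | 64.4% |
| 2 | 62.5% | 63.4% |
| 3 | 60.6% | 62.5% |
| 5 | 55.3% | 59.6% |

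At OR 3 the SE of the log odds ratio rose from 0.351 to 0.363, while the estimate moved from −0.778 to −0.826. The conditional odds ratio is a different quantity from the marginal one. The benefit therefore appears in the test and in the risk difference, not in the SE of the log odds ratio.

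**3. A count covariate under favourable assumptions.** Each patient has a visit rate drawn from a gamma distribution with shape k and mean μ visits per 6 months. The same rate generates the prior-year count and the follow-up count, and CGM halves it. The outcome is any return visit, and the covariate is log(1 + prior-year visits). The risk of any visit is 1 − (1 + μ/k)^(−k). For k = 0.5 and μ = 1.0 that is 1 − 3^(−0.5) = 42.3% in controls and 1 − 2^(−0.5) = 29.3% with CGM. With 1,500 trials per setting:

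| k | μ | Power unadjusted → adjusted |
|---|---|---|
| 0.5 | 0.6 | 46% → 56% |
| 0.5 | 1.0 | 47% → 64% |
| 1 | 0.6 | 60% → 63% |
| 1 | 1.0 | 68% → 75% |
| 2 (milder spread) | – | 80% → 81% |

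For k = 0.5 to 1 the SE ratio for the risk difference is 0.942 down to 0.835, a variance saving of 1 − 0.942² = 11% to 1 − 0.835² = 30%. For k = 2 it is 1 − 0.961² = 8%. With only 0.3 visits per 6 months and k = 0.5 to 1, the gain is 1 to 4 points. With no treatment effect, rejection stayed at 5.0–5.7%.

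**4. Relaxing those assumptions.**
- Past and future rates correlated 0.6 instead of identical (k = 0.5 to 1): SE ratio 0.951–0.982, so variance savings of 1 − 0.951² = 10% down to 1 − 0.982² = 4%. Power goes 48.4 → 52.4, 60.6 → 62.6 and 67.1 → 69.1.
- The same, with only 60% of prior visits visible (k = 1, μ = 1.0): 70.1 → 70.5.
- CGM rate ratio 0.8 instead of 0.5 (k = 1): 13.8 → 15.9 with identical rates (μ = 1.0), and 12.0 → 11.9 at correlation 0.6 (μ = 0.6).

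**The case against.** Four stronger readings are tempting, and the documents support none of them.

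- **That the plan rejects prior use as a covariate.** It is silent. It names no covariates at all for these models, and the lists for the other models are open-ended. The gap is an unspecified covariate set.
- **That prior use is known to be a strong predictor here.** Section 4 supports this only qualitatively, and from other institutions. No association, event rate or between-patient spread is given.
- **That precision is being given up for free.** In the planned logistic model, adjustment does not shrink the SE of the log odds ratio. To see a gain on the SE scale, the plan must also report a risk difference, which it does not now do.
- **That the large gains are to be expected.** They need a perfectly stable patient rate, wide spread and a halved 6-month visit rate, although the sensor is worn for at most 14 days (Section 9).

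It is also fair to say that prior ED visits may already be on the intake form, which is not in the text. These are secondary outcomes with no power claim, in a trial sized on attendance and DDS. All of this stands, and it limits the point to a modest improvement. It does not remove the point: no covariate is prespecified, the record is already being queried, and adjustment showed no material cost when there was no treatment effect or no association.

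**Conclusion.** The point holds as a low-cost improvement. No baseline covariate is named for the 6-month ED/EMS and hospitalisation models, and pre-index utilisation is an obvious and obtainable candidate.

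The size cannot be fixed from the documents. Under moderate association or imperfect stability of use, expect about 0 to 4 power points at 100 per arm. About 10 to 17 points arise only with very heterogeneous use (shape 0.5), a fully stable patient rate and a rate halved by CGM; shape 1 under the same conditions gave 3 to 7. If the true effect is small, the covariate will not rescue the comparison.

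A reader should not infer bias: randomisation keeps the unadjusted comparison valid.

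**What to change.** 1. Abstract the number of ED visits and the number of hospitalisations in the 12 months before the index visit, excluding the index visit. If the intake form already holds them, nothing new is collected. If not, they can be read retrospectively, but this must be done before medical record numbers are deleted once data collection is verified (Section 26).
2. State in Section 13 that log(1 + prior count) enters the ED/EMS model and the hospitalisation model as a fixed covariate. Do not treat the pre-index period as a repeated outcome, because every patient was selected for having an index visit.
3. Report the arm effect as a standardised risk difference alongside the conditional odds ratio, and say which is the estimand.

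The cost is at most two abstracted fields per patient and a few lines in the analysis plan, with no patient contact. Visits outside the health system may not be visible. That weakens the adjustment but does not bias it, since the count is fixed before randomisation.

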11. PROCEDURES INVOLVED*

Enrollment & Intake Visit of patient subjects:

- **Recruitment:** See Section 24. Research personnel will confirm subjects' pregnancy status by subject self report.
 - **Documents:**
 - **HIPAA Waiver**
 - **Info Sheet**
 - **Screening Log**
 - **Declined/Ineligible Log**
- **Consent:** See Sections 30 & 31
 - **Documents:**
 - **Consent**
 - **HIPAA Authorization**
- **Randomization:** Using the Redcap randomization module, patients will be randomized to the care coordination-only or care coordination plus CGM group
- **Master Code Contact Information:** Study Staff will obtain at least two ways (primary phone number and mailing address) to contact participants to schedule follow-up visits, completing a follow-up phone call if necessary, and to ensure the CGM equipment is returned.
 - **Documents:**
 - **Contact Info**
 - **Master Code**
- **Intake:** Study Staff will query EMRs to obtain the data points listed in the document below. Data collected will be verified with participants.
 - **Documents:**
 - **Intake Data- RA Facing**
 - **Intake Data- Patient Facing**
- **Device Training for intervention arm (CGM Arm only):** Half of the participants identified and enrolled as described above will be randomized to receive an unblinded CGM. We plan to use the 14-day Libre 2 CGM from Abbott. This device is a small disk (1.38 inches in diameter and 0.2 inches thick), and it weighs 0.18 ounces. After it is placed, a small (less than 0.4mm thick) sensor probe (not sharp) remains in the skin and can transmit continuous glucose data to a reader. The device can be submerged in water, and if it falls off, there will not be any significant bleeding. Study Staff will demonstrate the features and use of the CGM and sensor application (how the device should be worn, when it should be removed, the procedure to query the device for blood sugar readings using either a reader or smart phone application). After participants demonstrate an understanding of the use of the GCM, Study Staff will place the device on one of the participant's upper arms (patient choice) and monitoring will begin immediately after a

60-minute calibration period. They will be instructed to wear the CGM for two weeks continuously (including during sleep and hygiene), although they will also be advised that they can remove the sensor at any time if it causes any discomfort or distress. Subjects will not be removed from the study if they chose to remove the CGM. Participants will receive an informational sheet that explains the basic functionality of the CGM and lists Study Staff contact information in the event that they have questions about the CGM or its readings.

→ **Documents:**

- **CGM Information for enrolled patients (CGM arm only)**

- **Mobile Reader (CGM Arm only):** Study Staff will set up the Libre dedicated reader for subjects. Study Staff will demonstrate the features and use of the device and provide participants with an informational sheet that explains how and when to use the reader. Currently, Abbott, the company that manufactures the Libre 2 CGM system, is developing a mobile phone-based app to replace the reader. This app is under FDA review but is not yet approved. If it is approved between now and the end of enrollment, we will give participants the choice of using either the designated reader or their phone, if they possess a compatible phone.

→ **Documents:**

- **CGM Information for enrolled patients (CGM arm only)**

- **Education on managing out of range blood sugars:** All patients will receive information on how to respond to out of range blood sugars and emergency contact information

→ **Documents:**

- **Information sheet: Hyperglycemia**
- **Information sheet: Hypoglycemia**

- **Initial questionnaires: Patients will be administered** the five-question Problem Areas in Diabetes (PAID) scale as well as the 17-question Diabetes Distress Scale (DDS), which produces a total score and four subscale scores (emotional burden, regimen distress, physician distress, and interpersonal distress). Finally, patients will be administered several supplemental questions pertaining to their perceptions of their healthcare and barriers to obtaining optimal glycemic control.

→ **Paper Log:** Study Staff will administer these questionnaires on tablets shared with patients

▪ **Documents:**

- » **Problem Areas in Diabetes (PAID-5) scale/Diabetes Distress Scale and supplemental questions**

- **Diabetes Center of Excellence Care Coordination:** Study Staff will follow up with ED provider to ensure that patients' have clinically indicated referral to diabetes center of excellence

→ **Appointment scheduling:** RA will make an appointment for the patient before ED discharge, if possible. If this is not possible, RA will contact the patient after discharge to arrange a follow-up appointment.

Outpatient Blood Sugar Monitoring: The CGM will be worn on the participants' upper arm continuously for 14 days (or until it falls off or the patient decides to remove it)

[figure not shown]
Visit #1 (~Day 14-21 Post-Discharge of patient subjects)

- **Documents:**
 - **Visit Data (RA facing)**
 - **Problem Areas in Diabetes (PAID-5) scale/Diabetes Distress Scale and supplemental questions**
 - **Fact sheet for provider subjects**
 - **Provider satisfaction survey**
- **CGM Data:** Biosensor data will be downloaded and reviewed
- **Material Collection:** Study Staff will collect CGM readers
- **Compensation:** Participants will be offered \$10 worth of gift cards to a retail store for completing visit #1.
- **Provider Survey:** immediately following an encounter with a patient subject, the provider taking care of each patient will be contacted by the study team as potential provider subjects. Potential provider subjects subsequently will be sent an email solicitation to participate in a Redcap survey. A fact sheet will be provided with that email. The survey will consist of 4 questions pertaining to their satisfaction with patient subject care coordination and/or their CGM utilization. Providers may be sent multiple surveys if they see multiple subjects who are enrolled in the study. This is the only involvement of the provider subjects.
- **No Shows:** *RAs will reach out to subjects who miss their follow-up appointment to (1) help them reschedule and (2) ask that they fill out the post-intervention questionnaire via an online link (or mailed paper copy or via phone, if desired)*

Follow up Data Collection (~6 months Post-Discharge)

- **Documents:**
 - **6 month follow up datasheet**
- **Data Collection:** The study team will query the EHR to collect follow up data points about enrolled subjects

Figure 1: Procedural Flow Sheet

t

